6.1 SCREENING

For logistical purposes, up to 60 days will be allowed for screening to confirm that participants meet all selection criteria for the study. It is strongly encouraged that the screening period is minimized to the shortest possible duration whenever possible. The investigator (or an appropriate delegate at the investigator site) will obtain informed consent from each subject, caregiver/informant, and where appropriate, legally authorized representative in accordance with Subject Information and Informed Consent/Assent (where this is in accordance with local laws, regulations and ethics committee policy). The screening assessments may be separated out into more than one visit if required. Refer to the Schedule of Events for a tabular presentation for screening activities.

The following activities will be completed:

- Complete informed consent/assent process (where this is in accordance with local laws, regulations and ethics committee policy) resulting in a signed ICF(s) by the appropriate parties.
- Assign screening identification number.
- Complete MMSE to determine subject eligibility. If subject is eligible based on the MMSE, proceed with the remainder of screening visit in any order.
- ADAS-Cog
- The Columbia Suicide Severity Scale (C-SSRS)
- CDR (calculation of both global score and sum of boxes score global)
- Demographic information (i.e., sex, date of birth, race/ethnicity).
- Complete medical and surgical history, including family medical history of dementia.
- Record and review concomitant medications and any discontinued medication in the 60 days prior to the Screening visit.
- History of drug, alcohol and tobacco use.

- Complete physical and neurological exams.
- Rosen-Modified Hachinski Ischemia Scale
- Height and body weight.
- Vital signs: blood pressure (supine), pulse rate.
- Single 12-lead electrocardiogram (ECG).
- Review of inclusion and exclusion criteria.
- Blood and urine specimens for safety laboratory tests (serum chemistry, hematology, UA) will be collected, in addition to the following:
 - Serum glucose and HbA1c;
 - Hepatitis screens (including hepatitis B surface antigen, hepatitis B core antibody, hepatitis B surface antibody, and hepatitis C antibody);
 - Syphilis test. If positive, a standard confirmation test will be obtained;
 - Thyroid function (T3, T4, and TSH);
 - Vitamin B12 (and MMA if indicated, e.g., if serum B12 level <211 pg/mL);
 - Serum FSH concentrations in all female participants to confirm post-menopausal status and eligibility regarding non-child bearing potential;
 - Urine drug screen.
- Brain MRI performed at least 14 days prior to Month 0/Day 1 dosing; The MRI may also include gadolinium contrast if determined to be appropriate by the investigator. For subjects with a contraindication to MRI scanning (e.g. pacemaker), a CT scan will fulfill the requirements for assessing subject eligibility. Use of contrast is allowed upon investigator discretion.
- Upon completion of screening procedures, and prior to the Baseline visit, approval from the Sponsor on the Eligibility Assessment Form (EAF) must be obtained before proceeding to the Baseline visit.

Re-screening of a Participant

Participants previously screened but not dosed in another AD study, including a azeliragon study may participate in this study provided they meet the subject selection criteria. All screening data must be obtained within 60 days prior to the first dose of study medication.

Participants who had been screened and failed to join the study based on the following reasons are allowed to re-screen if the subject is beyond the original 60 day screening window. Participants do not have to repeat the MRI if dosing occurs within 90 days from the initial screening visit.

- Participants with Vitamin B12 below the normal limits at initial screening.

Participants must subsequently have been taking Vitamin B12 for at least 4 weeks after initial screen failure and have repeat B12 level within the normal range.

- Participants who are not on a stable dose of acetylcholinesterase inhibitors or/and memantine for at least 3 months prior to planned dosing may rescreen once they have reached 3 months of stable dosing of acetylcholinesterase inhibitors or/and memantine.
- Participants excluded because of potentially undiagnosed type 2 diabetes, provided that their disease and serum glucose values are now controlled and being actively managed, per the investigator's judgment.
- Hypertension discovered at screening that is subsequently actively managed and the blood pressure values are within acceptable limits.
- Subjects who have a CDR of 0 or an MMSE score >26 may rescreen upon approval of the sponsor's medical monitor. CDR scores greater than 1 or MMSE scores less than 21 may not rescreen. The time to rescreen a subject is up to the investigator but in any case may not be within 3 months with no upper time limit. They may rescreen only once. Subjects who score out of range are considered a screen fail, even if they are planning to rescreen.

6.2 STUDY PERIOD

6.2.1 Baseline (approximately Day -7-Day 1)

- ADAS-cog, MMSE, CDR-sb, ADCS-ADL, COWAT, CFT, Trail Making Test (Versions A and B), NPI, RUD Lite, DEMQOL-proxy
- C-SSRS.
- Review of inclusion and exclusion criteria including the results of the MRI scan.
- Brief physical and neurologic examination.
- Update concomitant medications.
- Weight.
- Assess baseline symptoms/adverse events.
- 12-lead electrocardiogram (ECG) (performed in triplicate).
- Vital signs: blood pressure (supine), pulse rate.
- Baseline FDG-PET (if applicable).
- Collect blood sample for plasma retention and storage.
- Blood sample for ApoE genotyping.
- Blood and urine sampling for safety labs including HbA1c.
- Collect blood samples for PK and PD.
- Randomize subject if eligible.
- Dispense study drug if eligible.
- Subject begins taking study medication in the clinic as soon as baseline procedures are completed (noted as Month 0 [Day 1] on [Table 1](#). Schedule of Activities).

If the baseline assessments are performed on more than one day, up to 7 days are allowed for completion of baseline procedures prior to subject randomization and dosing. The 7 day window will begin on the day that the first baseline assessment is performed and ends on the day when the subject is randomized and study drug is administered.

If it is necessary to extend the 7 day period for any other reason (e.g., schedule conflicts, patient/caregiver/informant illness, inclement weather) the Sponsor should be contacted for approval and the visit window may be extended up to 7 days. In this case, re-review of the inclusion/exclusion criteria and concomitant medications should occur within 7 days prior to the first dose to ensure that the patient continues to be appropriate for the study. Other baseline procedures may be repeated at the discretion of the Investigator, but are not required. The 60 day period from screening to first dose will remain in effect. Should the overall screening time exceed 60 days, re-screening will be required.

6.2.2 Month 1 (\pm 4 days)

- Telephone contact.
- Review and record new concomitant medications.
- Assess symptoms/adverse events by asking the participants to respond to a non-leading question such as “How have you been feeling?”
- Assess drug compliance with the question “Have you been taking your medication every day as instructed?”

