Three interim analyses were planned during the study. The first interim analysis was conducted 6 months after approximately 50% of participants had been randomized. This analysis was conducted for the purposes of safety and for informing internal development decisions. The second interim analysis was conducted 12 months after all participants were randomized to assess futility, as well as for safety and to inform internal development decisions. A third interim analysis to inform internal development decisions was to be conducted when all continuing participants completed the Month 18 visit.

The first pre-specified interim safety analysis revealed an increased frequency of AEs (concentration related and reversible upon discontinuation of treatment), in particular falls and confusion, in the 20 mg/day group relative to the 5 mg/day and

placebo groups. This was associated with a higher percentage of participants in the 20 mg/day group declining by ≥ 10 points on the ADAS-cog (relative to Baseline scores) at Months 3 and 6 (concentration related and stabilized/reversible upon discontinuation of treatment). These findings were not noted for the 5 mg/day group or the placebo group. On the recommendation of the Data and Safety Monitoring Board (IDMC), participants randomized to the 20-mg/day dose discontinued study drug, received a safety evaluation, and were asked to consent to continue to be followed for safety clinical and laboratory assessments.

Approximately 12 months after all participants were randomized, the second pre-specified interim analysis compared 5 mg/day and placebo for futility based on results of the completer population (i.e. those with available 18-month ADAS-cog data). Conditional power was computed based on assumed continuation of the observed trend.

While safety data raised no concerns, criterion for futility ($< 10\%$ conditional power to observe a significant difference between 5 mg/day and placebo at 18 months) was met and treatment was discontinued. The third interim analysis was not performed as the study was terminated due to futility. Attempts to replicate the futility analysis, using a data set representative of that which would have been used for the futility analysis (constructed from the final data set) have been unsuccessful with conditional probabilities consistently computed as $> 20\%$.

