4.0 SUBJECT SELECTION

4.1 INCLUSION CRITERIA

Subject eligibility should be reviewed and documented by an appropriately qualified member of the Principal Investigator's (PI's) study team before participants are included in the study.

1. Evidence of a personally signed and dated informed consent document indicating that the subject (or a legally authorized representative) and caregiver/informant has been informed of all pertinent aspects of the study. Participants must be able to provide assent (where this is in accordance with local laws, regulations and ethics committee policy) and assent may be re-evaluated during the study at regular intervals.
2. Participants and caregiver/informants who are willing and able to comply with scheduled visits, treatment plan, laboratory tests, and other study procedures.
3. The subject must have a reliable caregiver/informant with regular contact (i.e., 10 hours a week as combination of face-to-face visits and telephone contact acceptable) who will facilitate the subject's full participation in the study. Caregivers/informant must have sufficient subject interaction to be able to provide meaningful input into the rating scales administered in this study where caregiver/informant input is required, in particular the CDR and evidence of this should be documented in source documentation. Participants who reside in assisted living facilities are permitted provided that they meet caregiver/informant criteria.
4. Participants and caregiver/informants must be able to read, write, and speak the language in which psychometric tests are provided with visual and auditory acuity (corrected) sufficient to allow for accurate psychometric testing.
5. Males and females (of non-childbearing potential) ages ≥ 50 years of age at screening.

6. Diagnosis of probable AD, consistent with the criteria from the 2011 National Institute on Aging and the Alzheimer's Association workgroup (McKhann et al., 2011). Evidence of progression needs to be documented in source documentation at the time of screening based on review of prior medical records and/or information gathered from the subject or caregiver/informant(s). Biomarker evidence of the pathophysiological process or neuronal injury associated with AD should be documented if data is available in participant's medical records (not specifically measured for inclusion in this study).

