5.3.3 Compliance

Participants will bring all unused azeliragon/placebo capsules to each study visit. The number of capsules will be counted and documented. If more than expected are returned, participants will be asked to account for missed doses. If the number of capsules is less than expected, participants will be asked to account for the missing capsules (e.g., capsules that are lost vs. excessive dosing of study medication). Caregivers/Informants will be instructed to assist with monitoring dosing compliance.

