6.2.3 Month 2 (\pm 4 days)

- Telephone contact.
- Review and record new concomitant medications.
- Assess symptoms/adverse events and by asking the participants to respond to a non-leading question such as “How have you been feeling?”
- Assess drug compliance with the question “Have you been taking your medication every day as instructed?”

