7.3 SUICIDALITY ASSESSMENTS

The Columbia Suicide Severity rating Scale (C-SSRS) is a joint interview with the caregiver and patient that systemically assesses suicidal ideation and suicidal behavior (Posner et al, 2011). This scale will be administered at Screening Visit to evaluate life time suicide attempt, suicide behaviors, and other non-suicidal self-injuries. Positive responses on the C-SSRS will be mapped to the Columbia Classification Algorithm of Suicide Assessment (C-CASA) for classification and reporting using a standard algorithm.

At the Screening and Baseline Visit, the C-SSRS will be used to detect possible suicidality prior to dosing. If the patient's responses indicate: (1) the subject may have had suicide ideation associated with actual intent and/or plan in the past year, (2) any history of suicidal behavior in the past 10 years, (3) any lifetime history of

recurrent suicidal behavior the subject should be excluded. In the event that the subject answers “Yes” to the suicidal ideation items 4 or 5 of the C-SSRS or a history of suicidal behavior within the previous 10 years as indicated by a “yes” answer to any of the suicidal behavior items of the C-SSRS at the screening or baseline visit, that subject will not be eligible for inclusion in the study.

The C-SSRS will be used to assess suicide ideation or behavior at each study visit. Following dosing (after the Baseline / randomization visit, if there are “yes” answers on items 4, 5 or on any behavioral question of the C-SSRS, a professional suicide risk assessment should be done as soon as possible to determine whether it is safe for the subject to continue participation in the trial. A risk assessment will be done by a qualified mental health professional with expertise in the evaluation of suicidality in the elderly (e.g., psychiatrist, geriatrician or neurologist specializing in treatment of patients with AD) to determine whether it is safe for the subject to participate in the study. A change from baseline to a yes on any of these items will also constitute an AE and will be documented as such.

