8.6 DOCUMENTATION OF ADVERSE EVENTS

The condition of each study subject will be monitored throughout the study. Signs and symptoms of possible AEs may be observed by the staff, elicited by asking an open or indirect question (e.g., “How have you been feeling?”) or volunteered by the subject. All AEs, whether observed by the Investigator or clinical site staff, elicited from the subject, or volunteered by the subject, will be recorded. Data will include start and end dates, concomitant medications given for AE, Investigator-specified severity, relationship to study drug, and action taken. All AEs should be reported to the study Sponsor.

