## 4.2 Safety Variables

Safety is monitored in this study by collection of adverse events, vital signs, electrocardiography, and clinical laboratory measures. It is noted that all untoward events or experiences are reported as adverse events regardless of whether they are identified by clinical observation, subject reporting, physical examination, clinical laboratory test result, electrocardiography, or any other examination or test. It is noted that listings of vital signs, laboratory data, electrocardiograms (ECG), and all safety data from all other sources are reviewed by medically qualified individuals to ensure that safety signals are identified and reported in the analysis of the safety data from this study.

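### The mandatory caregiver/informant is never named as an adverse-event respondent, and at the Month 1 and 2 phone calls the patient's own recall is the only stated source

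*Protocol*

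**What the plan says.** **Adverse-event question.** Protocol 6.2.2 (Month 1) reads "Assess symptoms/adverse events by asking the participants to respond to a non-leading question such as" an open enquiry about how they have been feeling. The same bullet, with trivial variations, appears at Months 2 to 18, at follow-up (6.2.10) and at early termination (6.3). The caregiver is not mentioned in any of these bullets.

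**Recognised sources.** Protocol 8.6 states: "All AEs, whether observed by the Investigator or clinical site staff, elicited from the subject, or volunteered by the subject, will be recorded". Section 8.7 repeats this. SAP 4.2 says that untoward events are reported whether "identified by clinical observation, subject reporting, physical examination, clinical laboratory test result, electrocardiography, or any other examination or test". Neither list includes report by the caregiver.

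**Contacts before Month 3.** Table 1 shows telephone contacts at Days 30 and 60 and no clinic visit between Day 1 and Day 90. At both calls sites must also "Assess drug compliance with the question" of whether the medication has been taken daily. No respondent is named, but the question is worded to the patient.

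**Where the caregiver is used.** Inclusion criterion 3 says: "The subject must have a reliable caregiver/informant with regular contact", about 10 hours a week. The C-SSRS "is a joint interview with the caregiver and patient" (7.3). The CDR, ADCS-ADL and NPI draw on the informant (7.2.2, 7.2.3). On dosing, 5.3.3 says: "Caregivers/Informants will be instructed to assist with monitoring dosing compliance". At clinic visits with a capsule count, discrepancies are discussed with both the subject and the caregiver.

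**The concern.** The protocol treats self-report as insufficient for suicidality, function, behaviour and dosing, and brings in the informant for each. For adverse events it does not, although patients with memory impairment may not recall, or may not recognise, a fall or an episode of confusion. The Month 3 list of procedures shows the contrast: the drug-accountability bullet names the caregiver and the adverse-event bullet does not.

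The weak stretch is Day 1 to Month 3. Staff on a phone call cannot see a bruise or disorientation as they could in clinic. According to the Amendment 2 entry in the revision history, the calls replaced clinic visits, and what is learned on the call can prompt an unplanned visit. A silent call therefore also means no follow-up evaluation.

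Three things are at stake:
- the completeness and timing of the safety data that the IDMC reviews;
- the treatment-emergent psychiatric events that SAP 4.5 singles out for comparison between arms;
- consistency between sites, since some will ask the caregiver by habit and others will follow the text.

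**Working it through.** **1. Stated adverse-event sources, by period**

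| Period | Contact | Stated sources | Caregiver named for adverse events? |
|---|---|---|---|
| Day 1 to before Month 3 | Phone, Days 30 and 60 | Participant's answer to an open question | No |
| Months 3 to 18 | Clinic visit every 3 months | Same question, plus staff observation, brief examinations, ECG, laboratory tests and joint C-SSRS; NPI, CDR and ADCS-ADL at Months 3, 6, 12 and 18 | No, but the informant contributes to the C-SSRS and the scales |
| Follow-up | Clinic visit | Same question, observation, examinations, tests, C-SSRS and the NPI, CDR and ADCS-ADL | No, as above |

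Table 1 gives 9 clinic visits (screening, baseline, Months 3, 6, 9, 12, 15 and 18, follow-up). This matches the approximately 9 stated in Protocol 3.0, and none falls between Day 1 and Day 90.

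**2. Adherence in the same interval.** The capsule count at Month 3 covers all doses since Day 1 (5.3.3, 6.2.4). A pre-dose drug level is taken at Month 3 (7.4). Caregivers help to monitor dosing throughout (5.3.3). The SAP's example of non-compliance for the per-protocol set is a plasma level below quantification (SAP 3), not the phone answer. A missed dose can therefore be found in retrospect. What the calls can lose is time.

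**3. The Phase 2 signal.** Protocol 1.1.3 reports more adverse events, "in particular falls and confusion, in the 20 mg/day group", and adds that these findings were not noted at 5 mg/day or on placebo. This trial gives 5 mg/day.

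**4. Illustration of scale.** The plan gives no figure to reproduce: it states neither event rates nor a capture fraction. All of the following are assumptions: 18-month incidence 10% on placebo and 15% on active, 400 per arm, the same capture fraction *c* in both arms, and a nominal two-sided 5% comparison.

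Formula: z = c(0.15 − 0.10) / √[p̄(1 − p̄) × 2/400], with p̄ = 0.125c. The chance of a nominal signal is P(Z > 1.96 − z).

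| c | Patients recorded, placebo v active | z | Chance |
|---|---|---|---|
| 1.0 | 40 v 60 | 0.050/√(0.125 × 0.875 × 0.005) = 2.14 | 57% |
| 0.7 | 28 v 42 | 0.035/√(0.0875 × 0.9125 × 0.005) = 1.75 | 42% |
| 0.5 | 20 v 30 | 0.025/√(0.0625 × 0.9375 × 0.005) = 1.46 | 31% |

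The lower two rows apply the loss to all 18 months, which overstates a problem concentrated in the first 3. Suppose instead one event per affected patient, spread evenly over time, so that 3/18 = 1/6 fall before Month 3, with full capture afterwards. Capture of 50% in that window gives c = 1 − 0.5/6 = 0.917, z = 2.04 and a chance of 53%. Capture of 70% gives c = 1 − 0.3/6 = 0.95, z = 2.08 and 55%. The fall from 57% is then small.

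With equal capture the risk difference shrinks in proportion to *c*, while the risk ratio does not change.

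**The case against.** The strongest reply is that the text does not confine adverse events to what the patient says. Section 8.1 defines an adverse event without regard to who reports it, and 8.7.1 makes knowledge of a serious event, from whatever source, the trigger for reporting. The list in 8.6 reads as a statement of breadth, and nothing forbids a site from listening to the caregiver. Section 6.4 counts examinations and the neuropsychological batteries among the sources of safety data, and some of those batteries are informant-based. A change to yes on the specified C-SSRS items is itself an adverse event. Phase 2 linked the 20 mg/day signal to ADAS-cog decline, and the ADAS-cog is tested directly every 3 months from Month 3; SAP 1.7 says the IDMC's safety review includes it. The population is mild disease (MMSE 21 to 26).

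Most of this stands, and it rules out two stronger readings that a reader might infer. One is that events come only from the patient throughout the trial and will be under-recorded. Staff observation and the Month 3 onward procedures contradict the first part, and the documents neither show nor measure the second. The other is that missed doses go unrecorded; the Month 3 count, the drug level and caregiver monitoring answer that.

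The reply does not reach the two phone calls. None of the compensating procedures takes place between Day 1 and Month 3, and permission to accept caregiver information is not an instruction to ask for it.

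**Conclusion.** The concern holds as a gap in the stated elicitation rule. No adverse-event passage in either document directs sites to ask the caregiver/informant. The gap matters most at the Month 1 and 2 calls, where the participant's recall is the only stated source. Events such as falls or confusion may be missed or recorded late in that window; from Month 3 the gap is partly covered.

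Its size cannot be derived from the documents. The illustration shows direction only: 57% falling to 53–55% if the loss is confined to the first 3 months and events are evenly spread, or to 31–42% if it persisted for 18 months. Every rate and capture fraction is assumed, the assumed excess at 5 mg/day has no support in the documents, and SAP 5 makes safety evaluation descriptive, so no decision in the plan turns on such a test. A greater loss in one arm is conceivable, but the documents give no basis for putting a figure on it.

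For adherence, the most that can be said is that detection may be delayed until Month 3. The change is worth making because it is nearly free and uses a person already enrolled.

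**What to change.** - In Protocol 6.2.2 to 6.2.10 and 6.3, address the open adverse-event question to the participant and the caregiver/informant, above all at the Month 1 and 2 calls. Keep the non-leading form.
- In 8.6 and 8.7, add events reported by the caregiver/informant to the listed sources, and align SAP 4.2.
- At the Month 1 and 2 calls, put the compliance question to the caregiver/informant as well, and record who answered.

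The cost is protocol wording, one eCRF field for the respondent and a few minutes per contact. Slightly more adverse events will be recorded in both arms. If the change comes in while patients are on study, note the date, because events before and after it will have been elicited differently.
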